5.1 THERAPEUTIC/DIAGNOSTIC AGENTS

5.2 Ribavirin

Availability and Administration:

Generic ribavirin is commercially available as 200 mg, 400mg, and 600 mg tablets, which will be orally administered by the patients themselves. Ribavirin will be purchased from the hospital pharmacy. Tablets are supplied in bottles of 84 capsules (200 mg each). Ribavirin is available as blue-colored (shade depending on strength), capsule-shaped, film-coated tablets. Medication labels will comply with US legal requirements and be printed in English. They will supply no clinical information about the patient on the labels. The storage conditions for study drug will be described on the medication label. Ribavirin tablet may be taken with food or on an empty stomach.

Toxicities (> 10%):

Hematologic: anemia, thrombocytopenia, leukopenia, lymphopenia

Gastrointestinal: anorexia, nausea, diarrhea

Hepatic: elevated liver function tests

Pulmonary: dyspnea, cough

Reproductive: may be teratogen

Constitutional: fatigue, musculoskeletal pain

Dermatologic: alopecia, pruritis, rash

Neurologic: headache, dizziness

Endocrine and metabolic: hyperuricemia

Pharmacology:

Ribavirin oral tablet administration is characterized by rapid absorption with a t_{max} of approximately 2 hours, followed by rapid distribution and long terminal phases. Mean γ -phase half-life has been reported to be in the range of approximately 30 - 61 hours after a single dose, and 274 - 296 hours following multiple doses. Mean bioavailability is approximately 30 - 50%. Apparent plasma clearance is approximately 20 L/h. Population based pharmacokinetic models have identified factors associated with lower apparent clearance of ribavirin (female gender, higher age, and low body weight), but taken together these factors account for less than 30% of the variability in clearance (34, 67-69).

6.0 CRITERIA FOR SUBJECT ELIGIBILITY

6.1 Subject Inclusion Criteria

1. Prior diagnostic surgical or core needle biopsy, with confirmation of tonsil and/or base of tongue squamous cell carcinoma that is positive for expression of p16 and phosphorylated eIF4E, as determined by the Department of Pathology at MSKCC. The biopsy may be either of the tonsil, base of tongue, and/or an involved neck node. 2 unstained slides and/or tissue block must be available from the initial diagnostic biopsy

Positive expression p16 and phosphorylated eIF4E is defined as $\geq 30\%$ of tumor cells with cytological and/or nuclear staining

2. Age ≥ 18 and ≤ 65 years of age
3. Karnofsky Performance Status ≥ 80
- 4.

Adequate organ function, as follows:

Adequate bone marrow reserve: absolute neutrophil count (ANC) $\geq 1.5 \times 10^9/L$, platelets $\geq 160 \times 10^9/L$, hemoglobin $\geq 12 \text{ g/dL}$

Hepatic: total bilirubin within $1.5 \times$ upper limit of normal (ULN) ; alkaline phosphatase (AP), aspartate transaminase (AST) and alanine transaminase (ALT) $\leq 2.5 \times$ ULN

(Patients with Gilbert's syndrome as the cause of hyperbilirubinemia may be eligible if total bilirubin $\leq 2.5 \times$ UNL)

Renal: Serum creatinine $\leq 1.3 \text{ mg/dL}$. Patients with serum creatinine $> 1.3 \text{ mg/dL}$ may be eligible if creatinine clearance (CrCl) $\geq 55 \text{ mL/min}$ based on the standard Cockroft and Gault formula.

5. Patients of childbearing potential must have a negative serum pregnancy test within 14 days of treatment. Patients must agree to use a reliable method of birth control during and for 6 months following the last dose of study drug.
6. Ability to swallow oral medication.
7. Non-surgical patients: If primary radiation +/- chemotherapy (concurrent or sequential) is planned, patients must agree to undergo research biopsy after completion of ribavirin treatment.

6.2 Subject Exclusion Criteria

1. Prior chemotherapy or radiation for tonsillar or base of tongue squamous cell cancer
2. More than 10 pack-years of tobacco use
3. History of hemolytic anemia or thalassemia
4. Active infection or serious underlying medical condition that would impair the patient's ability to receive protocol treatment.
5. Current therapeutic anticoagulation with Coumadin (warfarin)
6. Current or prior treatment with ribavirin
7. Known active Hepatitis B or C
8. Any prior documented history of transient ischemic attack (TIA) or cerebrovascular accident (CVA)
9. New York Heart Association (NYHA) Grade II or greater congestive heart failure
10. Clinically significant peripheral vascular disease
11. History of unstable angina or myocardial infarction (MI) within the last 3 years

7.0 RECRUITMENT PLAN

Potential research subjects will be identified by a member of the patient's treatment team, the protocol investigator, or research team at Memorial Sloan-Kettering Cancer Center (MSKCC).

Patient recruitment will occur in medical oncology clinics of the Head and Neck Disease management team at main campus. If the investigator is a member of the treatment team, s/he will screen their patient's medical records for suitable research study participants and discuss the study and their potential for enrolling in the research study. Potential subjects contacted by their treating physician will be referred to the investigator/research staff of the study.

8.1 PRETREATMENT EVALUATION

All pre-treatment evaluations should be within 21 days prior to therapy, unless otherwise specified in this Section.

- Complete medical history including current medications, physical examination including evaluation of Karnofsky performance status.
- Pathology review at MSKCC must confirm diagnosis of tonsil and/or base of tongue squamous cancer that is positive for expression of phosphorylated eIF4E, at any time prior to treatment. Diagnostic biopsy may be of tonsil and/or involved neck node. 2 unstained slides and/or tissue block must be available from the diagnostic biopsy
- The following laboratory studies will be obtained within 21 days prior to therapy:
Complete blood count with white blood cell differential and platelet counts;
Comprehensive profile (including electrolytes, bicarbonate, blood urea nitrogen (BUN), creatinine, glucose, alkaline phosphatase, aspartate aminotransferase (AST), alanine aminotransferase (ALT), total bilirubin, total protein, albumin, and glucose); prothrombin time and activated partial thromboplastin time
- Serum pregnancy test for women of childbearing potential within 14 days prior to therapy.
- Electrocardiogram within 8 weeks prior to therapy
- Baseline cross-sectional imaging of the neck (CT neck or MR neck) within 8 weeks prior to therapy

9.1 TREATMENT/INTERVENTION PLAN

9.2 Clinical Plan

The clinical intervention in this study is ribavirin therapy for approximately 14 days. Ribavirin 800 mg/day is administered in divided doses, 400 mg PO qAM and 400 mg PO qPM. Details regarding evaluations during treatment are provided in Section 10.

9.3 Immunohistochemistry (IHC)

Each formalin-fixed and paraffin-embedded tissue specimen will be processed for IHC, consistent with established methods in our group (70). The time from tumor removal at surgery to formalin fixation should be 2 hours or less.

The avidin-biotin immunoperoxidase technique will be employed. Antigen retrieval with citric acid (0.01%) for 15 minutes under microwave treatment commonly precedes incubation with the primary antibody (usually overnight at 4°C). Primary antibodies to be used include anti-phospho eIF4E^{Ser209} (rabbit polyclonal, Cell Signaling #9741), anti-p16 (mouse IgG, clone E6H4, Dako #K5334), anti-p21 (mouse IgG, clone EA10, Calbiochem #OP64), anti-EGFR (mouse IgG, clone 31G7, Ventana #28-005), anti-HPV16 E6 (mouse IgG, clone C1P5, Santa Cruz #sc-460), and anti-E7 (mouse IgG, clone 8C9, Invitrogen #28-0006). Diaminobenzidine will be utilized as the final chromogen and hematoxylin will provide the nuclear counterstain.

If limited tumor tissue is available, the top priority immunostain will be phosphorylated eIF4E.

If sufficient tissue is available, exploratory analysis of additional biomarkers may be performed. For example, if immunohistochemistry does not provide definitive data regarding levels of E6, E7, and p53, expression may be explored with RT PCR using established methods (71, 72).

Technical difficulty or inability to obtain results with certain antibodies or samples will not be considered a protocol violation.

10.1 EVALUATION DURING TREATMENT/INTERVENTION

10.2 Description of Evaluations

Patients will be provided with a pill diary at the start of treatment (Appendix A), and will be required to bring a updated pill diary to each clinic visit. If patients miss any doses of ribavirin, this will not be considered a protocol violation but the investigator retains the discretion to remove patients from study for non-compliance.

Every attempt will be made for patients to have clinic visits and laboratory tests on the indicated dates. However, dates may need to be altered for medical or personal or logistical reasons. Clinic visits and laboratory studies may occur 3 days before or 3 days after the scheduled date, if need be. Additional clinical visits and laboratory studies may be scheduled if clinically necessary, per investigator discretion.

- On Day 1, routine laboratory studies are obtained: complete blood cell count and comprehensive metabolic panel. Patients undergo history and physical.
- Days 1 – 14, approximately: ribavirin 800 mg/day in divided doses, 400 mg q AM and 400 mg q PM. Typically, this will be administered as two 200 mg tablets qAM, and two 200 mg tablets qPM. Use of one 400 mg tablet (instead of two 200 mg tablets) is also allowed, at the discretion of the investigator.
- On Day 8, Routine laboratory studies are obtained: complete blood cell count and comprehensive metabolic panel. Patients undergo history and physical.
- Day 15 (approximately): Surgical plan is resection or research biopsy of the tonsil and/or base of tongue squamous cell carcinoma, possibly with neck dissection at the discretion of the surgeon. Patients will be considered done with treatment at time of surgery or research biopsy. As such, the surgical or biopsy procedure is considered off-protocol, and the surgery or research biopsy will be performed at the discretion of the investigator. The protocol provides no guidance nor places any restrictions regarding surgical management.

While every attempt will be made to schedule surgery or research biopsy on Day 15, the exact timing of surgery or research biopsy will be at the discretion of the surgeon. No ribavirin will be given after surgery or research biopsy.

- Post-operative (or post research biopsy) management will be per standard of care, off protocol.

10.3 Calendar of Events

	Baseline	Day 1	Day 8	Day 14	Day 15
History and Physical	X	X	X		
CBC, comp panel	X	X	X		
PT/aPTT	X				
EKG	X				
CT or MRI of neck	X				
Ribavirin		800 mg PO daily X 14 days			
Surgery or research biopsy					X
Adverse Events (AEs)		Continuous Monitoring for AEs			

^a This table shows approximate dates. Please see sections 9 and 10 for allowed variations in the timing of interventions and assessments

11.1 TOXICITIES/SIDE EFFECTS

This section provides guidelines for the clinical management of adverse events. The toxicities of ribavirin are presented in Section 5, and are listed again here:

Hematologic: anemia, thrombocytopenia, leukopenia, lymphopenia
Gastrointestinal: anorexia, nausea, diarrhea
Hepatic: elevated liver function tests
Pulmonary: dyspnea, cough
Reproductive: may be teratogen
Constitutional: fatigue, musculoskeletal pain
Dermatologic: alopecia, pruritis, rash
Neurologic: headache, dizziness
Endocrine and metabolic: hyperuricemia

Reporting requirements for adverse events are presented in Section 17.2.

All toxicities will be assessed according to CTC version 4. Dose reductions or drug stoppage are only required for those adverse events that the investigator feels are possibly, probably, or definitely related to ribavirin.

Subjects who take < 10 days of ribavirin prior to surgery will be considered inevaluable and will be replaced.

Any patient who requires dose reduction below 600 mg/day will be removed from study.

11.2 Hematologic Toxicity

The most common toxicity requiring dose reduction for ribavirin is anemia.

For any patient who experiences a fall in hemoglobin of > 2 g/dL (from Day 1 value), ribavirin dose will be decreased to 600 mg/day (200 mg qAM, 400 mg qPM). Any patients who develop a hemoglobin level of < 10 g/dL will be removed from study.

Any patient who develops a platelet count of < 100 K/mcL will be removed from study. Any patient who develops an absolute neutrophil count of < 1.0 K/mcL will be removed from study. Dose delays and dose reductions are not required for uncomplicated leukopenia or uncomplicated lymphopenia.

11.3 Non-Hematologic Toxicity

For any patient who develops grade 2 toxicity (felt to be definitely, probably, or possibly related to ribavirin), the investigator may either (a) reduce the dose of ribavirin to 600 mg/day, or (2) remove the patient from study. Any patient who develops toxicity of grade 3 or greater will be removed from study.

Even when the patient meets criteria for continued treatment at full dose per the protocol, the investigator retains the discretion to delay treatment and/or reduce dose (to 600

mg/day) if there are safety concerns and/or logistical issues. Any dose reductions not specified in the protocol should be discussed with the principal investigator.

12.0 CRITERIA FOR THERAPEUTIC RESPONSE/OUTCOME ASSESSMENT

The primary objective of this study is based on immunohistochemistry (IHC), not a therapeutic or radiologic outcome. For details regarding IHC methods, see Section 9.2. As a secondary endpoint, we wish to explore the feasibility of using pre and post treatment FDG-PET/CT scans to assess the metabolic effect of ribavirin in tonsillar and/or base of tongue squamous cell carcinoma.

The volume(s) of interest (VOI) from the MRI neck (or CT neck) images will be matched to the FDG PET/CT images. Matched VOIs will be analyzed by visual and semiquantitative analysis, using the attenuation-corrected PET emission images. For semiquantitative analysis, VOIs are placed over the areas of focal FDG uptake in the neck nodal metastases. The intensity of FDG uptake in these regions is measured using the standardized uptake value (SUV), normalized to body height. The maximum pixel SUV was recorded. The imaging data initially available in units of microcuries per milliliter per voxel are decay corrected to the time of injection and converted into SUV units (73).

PET images will be reconstructed from the initial data set using iterative reconstruction software and will be reoriented into transaxial, coronal and sagittal slices. Attenuation corrected scans will be read. The images will be reviewed in all standard planes (3-dimensional computer display) and a maximum intensity projection (MIP) image. At least 2 parameters will be investigated as measures of tumor response to therapy: SUVmax and SUVmean. Changes in these parameters between the baseline and follow up scans will be used as a measure of effect of study drug. The data analysis equipment and software for nuclear medicine imaging is continuously changing and evolving. As new imaging analysis methods are developed, we will apply those that are optimal to the imaging purpose.

13.1 CRITERIA FOR REMOVAL FROM STUDY

- Patients may be removed from the study for protocol non-compliance.
- If at any time the patient develops unacceptable toxicity he/she will be removed from study.
- Participants can be removed from the study at any time if the study doctor feels that it is in their best interest to do so.

14.0 BIOSTATISTICS

The primary endpoint of this pilot study is to explore if ribavirin therapy for 2 weeks decreases tumor expression of phosphorylated eIF4E among patients with tonsillar and/or base of tongue squamous cell carcinomas that expresses phosphorylated eIF4E.

Decision Rule: We would consider ribavirin to be interesting for further study in this patient population if we observe at least 4 patients (among 7) in which positive baseline expression of phosphorylated eIF4E becomes negative after ribavirin treatment.

Positive phosphorylated eIF4E overexpression is defined as $\geq 30\%$ of cells with cytoplasmic and/or nuclear staining by IHC (19, 24). With this 30% cutoff, the probabilities of observing at least 4 patients with negative post-treatment eIF4E expression among the 7 patients included in the study are listed below:

True probability that ribavirin inhibits eIF4E expression	Probability of observing the inhibition in at least 4 of the 7 patients
.40	.29
.50	.52
.60	.71
.70	.87
.80	.97

For each of the patients tested, we will tabulate pretreatment and posttreatment tumor expression of phosphorylated eIF4E, of molecules that are regulated by eIF4E (p16, p21, EGFR), HPV-16 oncoproteins (E6 and E7) and FDG-PET/CT scans, as well as percentage change between pretreatment and posttreatment levels.

Toxicity data (AEs, laboratory data and vital sign data) will be collected and listed individually per patient according to CTCAE version 4.0.

Subjects who take < 10 days of ribavirin prior to surgery (or research biopsy) will be considered inevaluable and will be replaced. The expected accrual rate is 1 to 2 patients per month, so we expect the study to be completed in 4 to 7 months.

Note: If the post-treatment tumor specimen cannot be obtained (eg, technical issues or patient withdraws consent) or if insufficient/inadequate material is available for immunostaining of phosphorylated eIF4E, the subject will be deemed inevaluable and will be replaced. If there is insufficient/inadequate tissue to perform the other immunostains discussed in the secondary aims, this would not be considered a protocol violation and the subject would not need to be replaced as long as the patient was evaluable for the primary endpoint of this pilot study.

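### In the Section 14.0 decision-rule table, the entry for a true probability of .50 is printed as .52; the exact value is .50

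*Combined protocol and SAP*

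**What the plan says.** Section 14.0 (Biostatistics) defines a positive tumour as one with at least 30% of cells staining for phosphorylated eIF4E. It sets a go rule: ribavirin merits further study "if we observe at least 4 patients (among 7) in which positive baseline expression of phosphorylated eIF4E becomes negative after ribavirin treatment". It then says that "the probabilities of observing at least 4 patients with negative post-treatment eIF4E expression among the 7 patients included in the study are listed below".

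The table has two columns. The first is headed "True probability that ribavirin inhibits eIF4E expression" and the second "Probability of observing the inhibition in at least 4 of the 7 patients". Its five rows are:

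| True probability | Printed probability of meeting the rule |
|---|---|
| .40 | .29 |
| .50 | .52 |
| .60 | .71 |
| .70 | .87 |
| .80 | .97 |

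The same section provides for patients whose post-treatment specimen is missing or inadequate: "the subject will be deemed inevaluable and will be replaced". Patients who take fewer than 10 days of ribavirin are also replaced. The denominator therefore stays at 7.

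**The concern.** With an odd number of patients, a per-patient probability of one half and a threshold just above the midpoint, meeting the rule and missing it are equally likely. The second row should therefore read .50, and .52 stands out without any calculation.

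This is a single-arm pilot with no hypothesis test, and the table is the plan's only statement of the operating characteristics of its go rule. A reader who wants to know how often an agent that converts half of tumours would be carried forward gets a wrong answer from this row. Because it is also the row that is easiest to check by eye, an error there may cast doubt on the rows that are right.

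**Working it through.** **Inputs, all from Section 14.0**

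- Number of patients: n = 7.
- Threshold: at least 4 conversions.
- Per-patient outcome: binary, from positive (at least 30% of cells) to negative.
- True conversion probabilities: p = .40, .50, .60, .70, .80.
- Inevaluable patients are replaced, so no dropout adjustment applies.

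**Formula**

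P(X ≥ 4) = 35 p⁴(1−p)³ + 21 p⁵(1−p)² + 7 p⁶(1−p) + p⁷, where 35, 21, 7 and 1 are the numbers of ways to choose 4, 5, 6 and 7 patients from 7.

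**Reproducing the plan's figures**

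| p | Exact P(X ≥ 4) | Two decimals | Printed | Agrees |
|---|---|---|---|---|
| .40 | .28979 | .29 | .29 | yes |
| .50 | .50000 | .50 | .52 | **no** |
| .60 | .71021 | .71 | .71 | yes |
| .70 | .87396 | .87 | .87 | yes |
| .80 | .96666 | .97 | .97 | yes |

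The four agreeing rows show that the table was built from the exact binomial with n = 7 and threshold 4, and reported to two decimals.

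**The .50 row by hand**

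At p = .50 each of the 2⁷ = 128 outcome patterns is equally likely. The patterns that meet the rule number 35 + 21 + 7 + 1 = 64, and 64/128 = .50 exactly.

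**A check inside the table**

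The threshold of 4 equals (7 + 1)/2, so the entries at p and 1−p must add to 1. The printed .40 and .60 rows do: .29 + .71 = 1.00. The .50 row is its own partner, so twice its entry must be 1. As printed, 2 × .52 = 1.04.

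**Could something else produce .52?**

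- *Rounding of the true probability.* Values that round to .50 run from .495 to .505 and give .489 to .511. To print as .52 the result must lie between .515 and .525, which needs p between .507 and .511.
- *An approximation.* At p = .50 the normal approximation gives .353 without a continuity correction and .500 with one. The Poisson gives .463.
- *Another sample size or threshold.* For n from 5 to 10 with thresholds from 2 to 7, no combination gives .52 at p = .50.

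**The case against.** The strongest objection is that nothing turns on this figure. The table describes the rule over a range of assumed probabilities. It sets no null rate, target rate or error limit, and the protocol does not single out the .50 row. A reader would judge a 7-patient exploratory pilot the same way at .50 or .52, and a 2-point gap is of the size often tolerated when power figures are checked. All of this stands as an argument about importance, and it keeps the point at the lowest level of priority.

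It does not make the figure right. A tolerance of that kind allows for unknown software or approximations. Here the method is evident from the other rows, the answer is exactly one half, and the neighbouring entries hold to two decimals.

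A second objection is that the discrepancy is one digit in a table taken from a PDF, so a misread character cannot be strictly excluded. The table is otherwise intact, with five complete and aligned rows, and nothing suggests a misreading. A look at the source page would settle it.

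**Conclusion.** The concern holds. The .50 row prints .52 where the exact value is .50, an overstatement of 2 percentage points in one of five rows. The other four rows are correct. The conclusion assumes only that the 7 patients respond independently with a common probability, which is the model that the other rows follow. No outside figure is needed.

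The error is minor and probably typographical. It does not bear on the 4-of-7 rule, the sample size or the 30% cutoff, and it says nothing for or against the adequacy of that rule.

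**What to change.** In the Section 14.0 table, change the entry for a true probability of .50 from .52 to .50, so that the column reads .29, .50, .71, .87, .97. The correction calls for no change to the other rows or to the decision rule.

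The cost is one figure in one table, which can be included in the next amendment. Sample size, analysis and study conduct are unaffected.

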15.0 RESEARCH PARTICIPANT REGISTRATION AND RANDOMIZATION PROCEDURES

15.1 Research Participant Registration

Confirm eligibility as defined in the section entitled Criteria for Patient/Subject Eligibility.

Obtain informed consent, by following procedures defined in section entitled Informed Consent Procedures.

During the registration process registering individuals will be required to complete a protocol specific Eligibility Checklist.

All participants must be registered through the Protocol Participant Registration (PPR) Office at Memorial Sloan-Kettering Cancer Center. PPR is available Monday through Friday from 8:30am – 5:30pm at [contact]. Registrations must be submitted via the PPR Electronic Registration System (<http://ppr/>). The completed signature page of the written consent/RA or verbal script/RA, a completed Eligibility Checklist and other relevant documents must be uploaded via the PPR Electronic Registration System.

